- g) Comparison of the duration of open label corticosteroid used to treat paradoxical TB-IRIS for participants that fulfilled INSHI TB-IRIS criteria. Duration in days will be compared using the Wilcoxon rank sum test.
- h) Comparison of the proportion of participants requiring hospitalization for paradoxical TB-IRIS event, within 12 weeks from randomization, using Chi-square test or Fisher exact test (as appropriate). This analysis will include only participants that fulfilled INSHI TB-IRIS criteria.
- i) Comparison of the proportion of participants requiring hospitalization for any cause (all-cause hospitalization), within 12 weeks from randomization, using Chi-square test or Fisher exact test (as appropriate). The total duration of hospitalization (in days) in each arm will also be compared using a zero-inflated Poisson model.
- j) Comparison of the proportion of participants who developed neurological manifestations of paradoxical TB-IRIS event (as decided by TB-IRIS review committee) using Chi-square test or Fisher exact test (as appropriate).

- k) Comparison of the C-reactive protein (CRP) concentrations in the two arms. CRP was measured at week 0, 2, 4 and 12. Values that fall below the detection limit will be replaced by half of the detection limit, i.e. 0.15. A mixed effects linear regression model on the log transformed CRP values with random intercept will be used to compare evolution of CRP over time between arms.
- l) Comparison of proportion of participants who die (all-cause mortality) within 12 weeks from randomisation between the two groups using Chi-square test or Fisher exact test (as appropriate).
- m) Comparison of proportion of participants who die and in whom death is attributed as due to paradoxical TB-IRIS within 12 weeks from randomisation between the two groups using Chi-square test or Fisher exact test (as appropriate). This will include only participants that fulfilled INSHI TB-IRIS criteria.
- n) Comparison of a composite endpoint of death, hospitalization, or hepatotoxicity (using the protocol-specified definition of Grade 3 or 4 increase in ALT or bilirubin) within 12 weeks of randomisation, using Chi-square test or Fisher exact test (as appropriate).
- o) Comparison of proportion of participants who develop other (non-TB) IRIS events within 12 weeks from randomisation, using Chi-square test or Fisher exact test (as appropriate).
- p) Comparison of quality of life assessment between the two arms at week 4 and at week 12. In the trial, the following measurements were performed: PROQOL-HIV, EQ-5D-3L, HIV symptom index and Karnofsky score. For EQ-5D-EL we will compare the proportion of patients in the different domain levels using the Chi-square test, and we will compare the means of the VAS score using the t-test or Wilcoxon rank sum test as appropriate. For the adapted ProQOL HIV the summary score per domain (adapted from [1]) will be compared using the t-test

or Wilcoxon rank sum test as appropriate. For the HIV-symptom index the frequency (proportion) and the severity of each symptom (score 1-2 vs score 3-4) will be compared using the Chi-square test. Because of multiplicity, Bonferroni correction will be applied in the analysis of HIV symptoms. Karnofsky score will be compared using the t-test or Wilcoxon rank sum test as appropriate.

- q) The cumulative proportion of participants who develop adverse events ascribed to TB treatment, ART or co-trimoxazole requiring interruption of one or more of these medications (for > 5 days) within 12 weeks of randomisation will be compared using Chi-square test or Fisher exact test (as appropriate).
- r) The cumulative proportion of participants who develop drug rash or drug-induced liver injury ascribed to TB treatment, ART or co-trimoxazole and requiring interruption of one or more of these medications (for > 5 days) within 12 weeks of randomisation will be compared using Chi-square test or Fisher exact test (as appropriate).

5. Analysis of secondary safety and tolerability endpoints

A number of secondary safety and tolerability analyses will be performed, all using the all-patients-treated approach (this excludes those participants who were randomized but never started study medication and/or ART).

- a) Comparison of proportion of participants in each arm who develop at least one of the pre-specified potential corticosteroid-associated adverse events within 4 weeks and within 12 weeks of randomization using Chi-square test or Fisher exact test (as appropriate). The proportion of participants in each group who develop individual potential corticosteroid-associated adverse events within 4 weeks and within 12 weeks of randomization will also be compared.

The pre-specified potential corticosteroid-associated adverse events are:

- New hypertension > 160/100
- New poor BP control on treatment > 160/100
- Hyperglycaemia (random glucose > 11.1 mmol/l)

- Hypomania/mania
- Depression
- Acne
- Epigastric pain
- Upper gastro- intestinal bleeding
- Cushingoid features
- New oedema
- Avascular bone necrosis

b) Comparison of laboratory safety bloods done at week 2, 4 and 12: sodium, potassium, creatinine, ALT, alkaline phosphatase, total bilirubin, glucose, haemoglobin, white cell count, neutrophil count, total lymphocyte count and platelets. Comparison of medians will be performed at each time point using the Wilcoxon rank sum test. The proportion of participants who develop an ACTG grade 3 or grade 4 abnormality in these blood tests will also be compared using Chi-square test or Fisher exact test (as appropriate).

c) Comparison of week 12 CD4 count and HIV viral load results. Comparison of medians will be performed using the Wilcoxon rank sum test. Proportion of participants with less than $2 \log_{10}$ drop in HIV viral load from screening to week 12 will be compared using the Chi-square test or Fisher exact test (as appropriate). Where screening viral load was too low to ascertain a $2 \log_{10}$ drop then an undetectable viral load at week 12 will be regarded as successful outcome.

d) Comparison of the proportion of participants who are diagnosed with other infections (AIDS-related, bacterial, fungal and viral) and malignancies (Kaposi's sarcoma) will be compared using Chi-square test or Fisher exact test (as appropriate). These will also be presented with individual listing. The proportion with severe infections (classified as any AIDS-defining (WHO stage 4) infection or invasive bacterial infection) will be compared in a separate analysis.

e) The proportion of participants with any clinical ACTG grade 1, 2, 3 and 4 adverse events (AEs) will be compared using Chi-square test or Fisher exact test (as appropriate). A similar comparison will be made for serious adverse events (SAEs) and adverse drug reactions (ADRs) attributed as definite, probably or possibly due to medication (the relationship between ADRs and medication has been determined by the study doctors and categorized as definitely not, unlikely, possibly, probably or definitely related to any medication).

In addition, a listing of AEs and SAEs categorized using MedDRA will also be presented. AEs and SAEs will be coded using the Medical Dictionary for Regulatory Activities (MedDRA) and will be reported based on MedDRA preferred terms and body systems. All AEs and SAEs will be analyzed based on counts of patients with a specific category and not on counts of individual adverse events.

All safety and tolerability analyses will be performed for the 12 week trial period, as well as a separate analysis restricted to the first 4 weeks from randomization. The reason for performing these analyses at 4 and 12 weeks, is that certain participants may commence open label corticosteroid (generally from 2-3 weeks onwards) so the 4 week analysis will exclude most of the safety events related to open label corticosteroid and more directly compare study prednisone versus placebo.

6. Pre-specified subgroup analyses relating to the primary endpoint

A number of pre-specified subgroup analyses of the primary endpoint will be performed using an ITT population. These subgroups will be

- a) Participants with screening CD4 count \leq 50 cells/ μ L
- b) Participants with screening CD4 count $>$ 50 cells/ μ L
- c) Participants with screening HIV viral load $>$ 100,000 copies/ml
- d) Participants with screening HIV viral load \leq 100,000 copies/ml
- e) Participants with microbiologically proven TB (TB culture and/or Xpert)
- f) Participants not diagnosed with rifampicin-resistant TB during follow-up.

7. Analysis of risk factors for TB-IRIS

As a tertiary analysis, we will assess possible risk factors for developing IRIS (age, gender, extrapulmonary TB, lymph node TB, TB diagnosis method, baseline CD4 count, baseline HIV viral load, CD4 count increase at 12 weeks, log HIV viral load decrease at 12 weeks, duration from TB treatment to ART initiation, urine LAM status, baseline CRP, and baseline haemoglobin, neutrophil, white cell counts and Karnofsky score) in addition to treatment arm in multivariable logistic regression model and Cox regression on cause-specific hazards.

8. Missing data and sensitivity analyses

For those participants lost to follow-up before week 12, data was obtained on vital status from telephonic contact or health service databases. However, it was not possible to ascertain their outcome in terms of TB-IRIS after loss to follow-up and they were thus regarded as not having developed TB-IRIS for the primary analysis. A sensitivity analysis will be performed where all participants lost to follow-up before week 12 will be assumed to have developed TB-IRIS.

9. Protocol deviations

A list of all protocol deviations, major and minor, has been compiled. These were defined according to the relevant trial SOP, and in accordance with guidance of the UCT Human Research Ethics Committee. These will be presented as supplementary material in the trial publication.

10. Week 28 and month 12 safety assessments

In the original trial protocol follow-up was planned until week 12 in all participants. After the publication of the IMPI trial findings, the DSMB recommended additional follow-up to ascertain development of cancers. A week 28 visit and 12 month visit or phone call were added. Where this was/is not possible then the patient's clinic or hospital notes are checked. These safety assessments are only for the purposes of ascertaining vital status and whether a cancer diagnosis has been made at these time points. These data are entered on a separate database from the main trial database. Follow-up of the last participant at one year will be completed in February

2017. The DSMB agreed that we could lock and unblind the main trial database before this, given that ascertainment of death and cancer at these time points is at low risk of being biased by knowledge of trial allocation.

11. Calculation of durations

Some participants had two or more hospitalisation, or two or more courses of open label corticosteroid. In such cases the duration of hospitalisation or open label corticosteroid was calculated by summing the number of days of each hospitalisation or of each open label corticosteroid course.

12. Publication

This Statistical Analysis Plan will be published on-line (eg. clinicaltrials.gov or PredART website), before locking and unblinding of database.

References

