14.1. Sample size calculation

Assuming 35% cumulative incidence of TB-IRIS in the placebo arm and a 50% reduction in TB-IRIS in the corticosteroid arm (ie. to 17.5%) and requiring 80% power to test for the difference in TB-IRIS incidence at a two-sided significance level of 5%, the sample size required would be 110 in each arm. We will aim to recruit 240 patients assuming loss to follow-up of 10%. The estimate of 35% incidence of TB-IRIS in the placebo arm corresponds to the findings of Blanc et al (110/332 (33%) of participants who started ART in the early arm in this trial had TB-IRIS events (32)) and a study we conducted at Brooklyn Chest TB Hospital in Cape Town (42% IRIS incidence [47]) and reflects that these will be patients at high risk for TB-IRIS due to low CD4 counts and short interval between TB treatment and ART start. Lawn and colleagues demonstrated in a retrospective study conducted in Cape Town that low CD4 count and shorter interval between TB treatment and ART initiation were the strongest predictors of TB-IRIS. In their study 70% of patients with a CD4 count < 100/μl who started ART within 30 days of TB treatment developed TB-IRIS [48].

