Tuberculosis (TB) is the most common opportunistic infection amongst HIV-infected patients starting antiretroviral therapy (ART) in developing countries and thus the most frequent form of immune reconstitution inflammatory syndrome (IRIS). Paradoxical TB-IRIS occurs in 4-54% of patients starting ART while on TB treatment and results in morbidity, hospitalisation, consumes health care resources and TB-IRIS may be fatal. We have previously demonstrated in a clinical trial that prednisone reduces morbidity when used for treatment of paradoxical TB-IRIS. This trial is a double-blind placebo-controlled trial of prophylactic prednisone (40mg/day for 2 weeks followed by 20mg/day for 2 weeks, started within 48 hours of initiating ART) in patients with TB who are identified as being at high risk for paradoxical TB-IRIS (starting ART within 30 days of initiating TB treatment and $CD4 \leq 100/\mu L$). The trial has enrolled 240 participants, randomised 1:1 (prednisone:placebo). The primary endpoint is development of paradoxical TB-IRIS, defined using an international consensus case definition. The trial is powered to determine a reduction in TB-IRIS events. The trial conduct is described in the Protocol.

These planned analyses will be performed by the statistician(s) at the Clinical Trials Unit of the Institute of Tropical Medicine (Antwerp) in collaboration with the investigators at the University of Cape Town and at ITM (Antwerp). The analysis results will be described in a statistical analysis report, to be used as the basis of the primary research publications. This analysis plan describes statistical methods for the primary and secondary objectives of the study as defined by protocol. Additional analyses may be performed but are not covered by the current analysis plan.

2. Baseline characteristics

The number of patients screened and enrolled or excluded will be summarized by reason for exclusion. For the patients enrolled in the study, the number of patients discontinued or lost- to follow-up will be tabulated by reason and visit of study discontinuation. This information will be summarized in a CONSORT flow diagram.

Patients in each treatment group will be described with respect to baseline

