All these narratives were reviewed by an independent TB-IRIS review committee comprised of 3 expert clinicians not active at the clinical site. This review was performed in accordance with PREDART SOP 2016/19 ("PredART trial: Review of suspected TB-IRIS cases by independent endpoint review committee). Individual decisions regarding whether the case fulfilled the INSHI case definition were made, followed by consensus seeking according to the SOP to derive a final committee decision whether the case fulfilled the INSHI case definition for paradoxical TB-IRIS – this will be used as the primary endpoint event for the PredART trial.

The statistical analysis for the primary endpoint will compare the proportion of participants in the prednisone arm who fulfilled the INSHI paradoxical TB-IRIS definition to the proportion in the placebo arm, within 12 weeks from randomization. The analysis will be an intention to treat (ITT) analysis including all 240 participants randomized. A Chi-square test or Fisher exact test (as appropriate) will be used. A p-value of less than 0.05 will be regarded as significant for the primary endpoint analyses, and all other analyses performed. In addition, the relative risk of TB- IRIS will be estimated together with a 95% confidence interval. The primary hypothesis of the study is that the proportion of patients developing paradoxical TB-IRIS within 12 weeks of starting ART, as determined by the INSHI case definition and confirmed by the endpoint review committee, will be lower in patients randomized to prednisone compared to patients randomized to placebo.

In addition, as a secondary analysis, an all-patients-treated approach will be performed excluding those participants who were randomized but never started study medication and/or ART.

4. Analysis of secondary efficacy endpoints

A number of secondary efficacy analyses will be performed, all on the ITT population and the all-patients-treated population:

- a) Comparison of proportion of participants who fulfil at least one INSHI major criterion for diagnosis of paradoxical TB-IRIS in each arm. This will be done using Chi-square test or Fisher exact test (as appropriate).

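### The SAP calls p<0.05 significant for the primary endpoint and all other analyses; apart from HIV symptoms, no multiplicity control or nominal label covers the secondary, safety and subgroup tests

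*Supplement*

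**What the plan says.** SAP section 3 defines one primary endpoint, adjudicated paradoxical TB-IRIS within 12 weeks, compared once in the intention-to-treat population. It then gives the rule: "A p-value of less than 0.05 will be regarded as significant for the primary endpoint analyses, and all other analyses performed". For the primary endpoint it also asks for a relative risk with a 95% confidence interval.

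SAP section 4 opens with "A number of secondary efficacy analyses will be performed, all on the ITT population and the all-patients-treated population" and lists items a to r. Section 5 lists five safety items, most with many sub-tests, and repeats the safety analyses for the first 4 weeks. Section 6 lists six subgroups, and section 7 a set of candidate risk factors. These sections name tests or models but ask for no confidence intervals. None gives a testing order or an alpha allocation, or says that its p-values are nominal.

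The one exception is in section 4, item p: "Because of multiplicity, Bonferroni correction will be applied in the analysis of HIV symptoms".

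The protocol (version 1.4, section 14.1) sizes the trial on the primary comparison alone. Sections 14.2.4 to 14.2.6 set no significance level for other endpoints.

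**The concern.** This is a written rule, so the plan cannot be read as silently treating the secondary results as exploratory. An analyst who follows it will label any secondary, subgroup or laboratory result with p<0.05 as significant, on the same footing as the primary.

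Items a to c of SAP section 4 are variants of the TB-IRIS outcome: major criteria only, committee-judged cases outside the consensus definition, and sustained cases. Item d is the use of open-label corticosteroids to treat it. If the primary result is null or borderline, several closely related outcomes could each carry the word. The protocol expects the findings to inform practice and guidelines and the design of a mortality trial (section 3.7), so a chance benefit or harm labelled significant could travel some way.

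Item p shows that the authors recognised multiplicity and dealt with it in one family only.

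**Working it through.** **The plan's own figure.** Protocol 14.1 assumes 35% against 17.5%, 80% power and two-sided 5%, and concludes that "the sample size required would be 110 in each arm".
- Mean proportion: (0.35 + 0.175)/2 = 0.2625.
- Uncorrected n = [1.96·√(2·0.2625·0.7375) + 0.842·√(0.35·0.65 + 0.175·0.825)]² / 0.175² ≈ 98.05, so 99 per arm.
- With continuity correction: (98.05/4)·[1 + √(1 + 4/(98.05·0.175))]² ≈ 109.2, so 110 per arm.

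The stated figure is reproduced. It spends 5% on one comparison and reserves nothing for any other.

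**Count by lettered item.** Items a to r make 18.
- Expected false positives if all nulls are true: 18 × 0.05 = 0.9.
- Chance of at least one, if independent: 1 − 0.95^18 = 60%.
- Chance of at least three, if independent: 6%.

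Many items concern TB-IRIS in the same participants. Positive correlation lowers the 60% but leaves the 0.9 unchanged.

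For comparison, the base HIV symptom index has 20 items (protocol 21.1). Taking 20 tests as an assumption, since the trial extends the list, the uncorrected chance of at least one is 1 − 0.95^20 = 64%. Bonferroni at 0.05/20 = 0.0025 brings it to 4.9%. The family that the SAP chose to correct is thus about as exposed as the lettered list that it left alone.

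**Count by individual sub-test** (one population, 12-week safety window, HIV symptoms and subgroups excluded).

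| Source | Tests |
|---|---|
| Section 4 without item p (17 items; item i has two tests) | 18 |
| Item p at two visits: 5 EQ-5D domains, VAS, 8 PROQOL-HIV domains (protocol 21.1), Karnofsky = 15 × 2 | 30 |
| 5a: 11 steroid events plus any event | 12 |
| 5b: 12 analytes × 3 visits (medians) | 36 |
| 5b: grade 3 or 4, by analyte | 12 |
| 5c: CD4, viral load, proportion with a small viral-load drop | 3 |
| 5d and 5e (minimum reading: 2 + 3) | 5 |
| Total | 116 |

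At full 5% size: 116 × 0.05 = 5.8 expected.

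**Allowance for sparse binary outcomes.** All 2×2 tables were enumerated at 120 per arm, with the same event rate in both arms and Fisher's exact test at 0.05:

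| Event rate | Actual size |
|---|---|
| 1% | 0.1% |
| 2% | 0.7% |
| 5% | 2.1% |
| 10% | 2.9% |

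The SAP allows chi-square where appropriate, and its size is close to 5% once events are common.

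- Taken at 5%: 38 laboratory medians (36 plus CD4 and viral load), 30 quality-of-life tests, and 5 non-binary efficacy tests (items e, f, g, k and hospital days in i) make 73. 73 × 0.05 = 3.65.
- Remaining binary tests: 116 − 73 = 43. At an average size of 1% they add 0.43, at 2.1% about 0.90, and at 5% 2.15.
- Total: about 4.1, 4.6 and 5.8, so roughly 4 to 6.

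The six subgroups would add at most 6 × 0.05 = 0.3. The risk-factor models of section 7 are not counted.

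**The case against.** The strongest case is that the confirmatory inference is intact. There is one primary endpoint, one intention-to-treat comparison and one 5% test. Everything else is labelled secondary, subgroup or tertiary, the protocol calls the trial proof-of-concept, and unadjusted secondary and safety p-values are common practice. For safety, strict adjustment could hide harm. All of this stands. It means that the fault lies in attaching the word significant to every test, and not in the absence of adjustment as such. It does not answer a sentence that expressly puts all analyses on the primary's footing.

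Several stronger readings are tempting but are not supported:
- *That nothing is corrected.* Item p corrects the HIV symptoms, and that specific rule qualifies the general sentence.
- *That each secondary claim has an error rate far above 5%.* Each single test stays at about 5% or less; only the chance of at least one false positive across the set is higher.
- *That a secondary result may replace a null primary.* No rule in the SAP says so.
- *That the two analysis populations double the problem* (1 − 0.95^36 = 84%). The all-patients-treated set only drops participants who never started study drug or ART, so the two analyses are near duplicates.
- *That six or seven or more false positives should be expected.* This needs the 4-week repeats (about 145 tests, 7.25 expected) or similar counts, every null true, and full 5% size for rare events. The protocol itself reports steroid effects on CRP and glucose (section 3.3), so some nulls are probably false.

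**Conclusion.** The point holds as one about the decision rule. Outside the HIV symptom list, the SAP labels any p<0.05 as significant with no multiplicity control and no statement that the p-values are nominal. The primary endpoint is not affected.

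The size depends on the counting unit. By lettered efficacy item, about one false positive is expected (0.9), with a chance of at least one of up to 60%. *Several* is justified only when individual sub-tests are counted, at roughly 4 to 6 of about 116. These figures assume that all nulls are true and that the sub-test counts follow a minimum reading of items 5d and 5e. The 60% also assumes independence and is best read as an upper figure. The sparse-event allowance rests on assumed event rates of 1% to 10%, because the documents give none for most safety outcomes.

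**What to change.** Replace the sentence in SAP section 3 with:

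> A two-sided p<0.05 is the criterion for statistical significance for the primary endpoint only. Secondary efficacy, subgroup, risk-factor and safety analyses are reported as effect estimates with 95% confidence intervals; their p-values are nominal, unadjusted for multiplicity (except HIV symptoms, Bonferroni), and are not described as statistically significant. Safety signals are judged on estimates, intervals and clinical importance.

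This keeps every planned analysis and does not raise the bar for seeing harm. It needs no new data, no larger sample and no change of procedure. Confidence intervals must be added to the outputs of sections 4 to 7. The real cost is that fewer secondary results can be called significant.

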Thirdly, on the condition that multi-group scalar invariance is proven (see above), the QOL measures will be used as one of the outcome measures in the clinical trial comparing the use of prednisone with placebo in patients at high risk of TB-IRIS. Comparison of means (SD) and medians (IQR) of the scores (total and domain scores) obtained by the different tools in the placebo and the intervention group will be done using Wilcoxon rank sum, chi-square and Fisher's exact tests, as appropriate.

Table: Summary of Quality of Life assessments to be performed within the clinical trial

| Instrument | Method | Interviewees |
|---|--|---|
| PROQOL-HIV (including “TB” in the questions, next to “HIV”) | Self-administered questionnaire (or administered by counselor) | All participants at week 0, 4 and 12 visit |
| EQ-5D-3L | Self-administered questionnaire (or administered by counselor) | All participants at week 0, 4 and 12 visit |
| HIV-symptom index (complemented with specific symptoms related to IRIS and steroid side effects) | Self-administered questionnaire (or administered by counselor) | All participants at week 0, 4 and 12 visit |
| Karnofsky score | Score assigned by investigator in discussion with participant | All participants at week 0, 4 and 12 visit |
| Respondent debriefing interviews | In-depth interview conducted by an investigator specifically involved in QoL substudy with assistance of counselor for translation | 10-15 interviews with a random sample of participants |

REFERENCES

2. [name], Lawn SD, Scano F, Maartens G, French MA, Worodria W, Elliott JH, Murdoch D, Wilkinson RJ, Seyler C *et al*: **Tuberculosis-associated immune reconstitution inflammatory syndrome: case definitions for use in resource-limited settings.** *Lancet Infect Dis* 2008, **8**(8):516-523.
3. [name], Wilkinson RJ, Morroni C, Pepper DJ, Rebe K, Rangaka MX, Oni T, Maartens G: **Randomized placebo-controlled trial of prednisone for paradoxical tuberculosis-associated immune reconstitution inflammatory syndrome.** *AIDS* 2010, **24**(15):2381-2390.

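### The continuous quality-of-life scores and week-12 CD4 are compared without their collected baseline values, which is valid but costs precision; a modest supportive adjustment is also missing for the primary endpoint

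*Supplement*

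**What the plan says.** **Quality of life.** SAP section 4(p) plans a "Comparison of quality of life assessment between the two arms at week 4 and at week 12". EQ VAS, the ProQOL-HIV domain scores and Karnofsky are each compared by t-test or Wilcoxon test. EQ-5D levels and symptom items are compared by chi-square. The table in protocol v1.4, section 21.2, gives the schedule for every instrument as "All participants at week 0, 4 and 12 visit", so a week-0 value exists for each score.

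**CD4 and viral load.** SAP section 5(c) plans a "Comparison of week 12 CD4 count and HIV viral load results", using medians and the Wilcoxon test. It also compares the proportion with less than a 2-log drop in viral load from screening, which does use the screening value.

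**Primary endpoint.** SAP section 3 says: "A Chi-square test or Fisher exact test (as appropriate) will be used". An unadjusted relative risk with its confidence interval goes with it. Protocol section 14.1 cites a retrospective study in which "low CD4 count and shorter interval between TB treatment and ART initiation were the strongest predictors of TB-IRIS". Protocol section 4.2 describes 1:1 randomisation in blocks of 8 and states no stratification factor.

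**Nearest provisions.** SAP section 2 will note any baseline imbalance but attaches no analysis to it. Section 6 has subgroups by screening CD4 and viral load. Section 7 has a tertiary risk-factor model that includes treatment arm. The sensitivity analysis in section 8 concerns loss to follow-up only.

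**The concern.** Participants differ in quality of life and CD4 before treatment starts. A comparison of follow-up scores alone leaves those known differences in the error term. Intervals are then wider than they need be, and an effect on a secondary endpoint is easier to miss.

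The same applies more weakly to the primary endpoint. Two predictors of TB-IRIS are named and known before randomisation, neither is balanced by design, and no clean overall effect adjusted for them is planned. If the arms turn out to differ on CD4, any adjustment chosen after unblinding would be post hoc.

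**Working it through.** **1. The plan's own sample size.** Inputs from protocol 14.1: 35% vs 17.5%, two-sided 5%, "requiring 80% power to test for the difference".
- Mean risk 0.2625; difference 0.175.
- n = [1.960·√(2·0.2625·0.7375) + 0.842·√(0.35·0.65 + 0.175·0.825)]² / 0.175² = 98.04, so 99 per arm.
- With continuity correction: (98.04/4)·[1 + √(1 + 4/(98.04·0.175))]² = 109.2, so 110 per arm, as stated.
- At 120 per arm, power is 87.4% by chi-square and 84.6% by exact Fisher test. The unadjusted primary analysis is therefore adequately powered on the plan's assumptions.

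**2. Continuous scores.** ANCOVA on the baseline value multiplies the variance of the arm difference by 1 − ρ², where ρ is the baseline-to-follow-up correlation. The documents give no ρ; 0.3 to 0.6 is assumed. Equivalent totals are 240/(1 − ρ²), rounded up. The detectable difference (80% power, 110 per arm) is 2.80·√(2/110) = 0.378 SD unadjusted, multiplied by √(1 − ρ²) when adjusted.

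| ρ | Variance reduction | Interval narrower by | Equivalent total | Detectable difference |
|---|---|---|---|---|
| 0.3 | 9% | 5% | 240/0.91 = 264 | 0.360 SD |
| 0.5 | 25% | 13% | 240/0.75 = 320 | 0.327 SD |
| 0.6 | 36% | 20% | 240/0.64 = 375 | 0.302 SD |

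**3. Primary endpoint.** Assume equal halves at CD4 ≤50 and >50, placebo risks of 45%/25% (case 1) or 50%/20% (case 2), and both risks halved on prednisone. Each case averages to the plan's 35% and 17.5%. Variances below are multiplied by the number per arm.
- Unadjusted: 0.2275 + 0.1444 = 0.3719.
- Standardised over CD4 stratum: mean within-stratum variance in each arm, plus half the between-stratum variance of the risk difference.
- Case 1: 0.2175 + 0.1419 + 0.0025/2 = 0.3606. That is 3.0% lower, and 240·0.3719/0.3606 gives 248 participants, rounded up.
- Case 2: 0.2050 + 0.1388 + 0.0056/2 = 0.3466. That is 6.8% lower, like 258 participants.

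As a wider check, a simulation at 120 per arm (1,500 runs per setting) used one continuous baseline risk score. With an assumed AUC of 0.64 to 0.79, the variance of the risk difference fell by about 4% to 19%. With a score unrelated to outcome there was no gain (variance ratio 1.01).

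**4. Do sections 6 and 7 already supply this?** Section 6 gives effects within CD4 strata and does not combine them into an overall adjusted effect. Section 7 includes the 12-week changes in CD4 and viral load. These arise after randomisation, so the arm coefficient is not a clean baseline-adjusted effect. It also lists 16 factors plus arm. The design rates imply 42 + 21 = 63 events, or 63/17 = 3.7 per term if all are entered.

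**The case against.** The strongest reply is that nothing here is an error. Under randomisation the unadjusted chi-square or Fisher test keeps its error rate, matches the sample size calculation and is simple to report. Chance imbalance is already allowed for in the p-value and the confidence interval. Eligibility limits CD4 to 100 or below and TB treatment to under 30 days, which narrows the range of both predictors. A second primary result could also blur which one decides. All of this stands, and it is why the adjusted primary estimate should be supportive only.

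A reader might infer more than the documents support:
- **That CD4 and the treatment interval are ignored outside the tertiary model.** Section 6 analyses the primary endpoint by screening CD4.
- **That section 5(c) makes no use of screening values.** The 2-log-drop comparison does.
- **That the predictors named in protocol 14.1 also predict quality of life.** That statement concerns TB-IRIS only. The quality-of-life case rests on each score having its own unused week-0 value.
- **That the primary gain is 4% to 10%.** That follows from applying the placebo variance, 0.2275, to both arms (0.01/0.2275 and 0.0225/0.2275). With the plan's own 17.5% on prednisone it is 3% to 7%.

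ANCOVA also does not suit the EQ-5D levels or symptom items, which are categorical. Week-12 viral load would need a rule for results below detection, so its comparisons are better left as planned.

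**Conclusion.** The point holds as a loss of efficiency; the planned tests remain valid. It is strongest for ProQOL-HIV domain scores, EQ VAS, Karnofsky and week-12 CD4, where a baseline value of the same measure is collected and unused. The gain is 9% to 36% of variance if the correlation is 0.3 to 0.6, and it would be smaller if baseline predicts follow-up poorly. For the primary endpoint the gain is modest, about 3% to 7%, and rests wholly on the assumed CD4-stratum risks, equal halves and halving on prednisone. The main benefit there is an adjusted estimate fixed in advance should the arms differ on CD4 or treatment interval.

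A reader might conclude that the primary result would be biased, or that the primary test should be replaced. The documents support neither.

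**What to change.** Amend the SAP wording before the database is unblinded.

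- **Sections 4(p) and 5(c):** analyse ProQOL-HIV domain scores, EQ VAS and Karnofsky at weeks 4 and 12 by ANCOVA on the week-0 value, and week-12 CD4 by ANCOVA on the screening value. Use rank-based ANCOVA if skewed. Report the adjusted difference with its 95% confidence interval. Leave the EQ-5D levels, symptom items and viral load comparisons, including the 2-log drop, as planned.
- **Section 3:** state that the unadjusted chi-square or Fisher test alone decides the primary hypothesis. Add one supportive relative risk and risk difference, each with a 95% confidence interval, standardised from a logistic model containing only arm, screening CD4 and days from TB treatment start to randomisation. Counting to randomisation keeps participants who never start ART in the analysis.

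No new data are needed. The cost is slightly more analysis code. The plan already models CRP longitudinally from week 0 in section 4(k), so modelling a repeated measure with its baseline is not new to it.
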